# Abbreviations

- ARVC arrhythmogenic right ventricular cardiomyopathy
- CMRI cardiac magnetic resonance imaging
- DCC Data Coordinating Center
- ECG electrocardiogram
- ICD implantable cardioverter-defibrillator
- IDS Investigational Drug Services
- VF ventricular fibrillation
- VPBs ventricular premature beats
- VT ventricular tachycardia

# 1. PURPOSE OF THE STUDY AND BACKGROUND

## 1.1. Background

## 1.1.1. Arrhythmogenic Right Ventricular Cardiomyopathy

Arrhythmogenic right ventricular cardiomyopathy (ARVC) is an inherited cardiomyopathy characterized by fibrofatty replacement primarily of right ventricular muscle. The resultant heterogeneous structure of the RV myocardium results in ventricular arrhythmias, including ventricular premature beats (VPBs), nonsustained or sustained ventricular tachycardia (VT) or ventricular fibrillation (VF). ARVC is uncommon disorder (1 in 5000 individuals) but may account for up to 20% of cases of sudden death among young individuals (Marcus et al. 1982, Calkins 2013, Corrado 2017). As shown in Figure 1 from the Johns Hopkins and the Dutch ARVC registries described by Bhonsale et al. (2015), about 60% pf ARVC patients develop life-threatening arrhythmic event or SCD by the age of 30 years. Figure 2 from an Italian cohort described by Mazzanti et al. (2016), about 20% died from cardiovascular causes by the age of 30 years.

[figure not shown]
[figure not shown]

Figure 3 from the North American ARVC Registry, which enrolled newly diagnosed ARVC patients, showed that about 40-50% of men and women with ARVC and implanted ICD developed arrhythmic events or did die within 2 years after implant of the device. The risk of fast VT, VF or

death is higher in males than females: 27% vs. 11%, respectively at 2 years (Choudhary et al. 2016). The John Hopkins and Dutch registries showed significantly higher lifetime risk of sustained arrhythmias or SCD in 312 males than in 256 females (Bhonsale et al. 2015).

ARVC is caused by mutations in the genes encoding for desmosomal proteins which are found in about 50% of patients (Groeneweg et al. 2015). In the remaining 50%, genes are unknown. Desmosomal genes include: plakophilin-2 (PKP2), plakoglobin, desmoplakin, desmoglein-2, and desmocollin-2 but mutations in several non-desmosomal genes including phospholamban and TMEM43-encoding transmembrane protein 43 have also been reported to cause ARVC (Bhonsale et al. 2015, Groeneweg et al. 2015). In the Johns Hopkins and the Dutch ARVC registry, among 575 ARVC patients with known mutations 463, (80%) carried a single copy of a *PKP2* mutations (Bhonsale et al. 2015).

Prevention of sudden cardiac death with implantable cardioverter defibrillator (ICD) is the primary management in ARVC. Several studies of ARVC patients who received an ICD showed appropriate interventions during follow-up in about 50% of patients (Dalal et al. 2005, Corrado et al. 2010, Bhonsale et al. 2011, Link et al. 2014). Of these, approximately 40% were considered life-saving based on the presence of rapid VT/VF with a rate of >240 bpm. Predictors of appropriate therapy included previous VF arrest, syncope, severe RV dilation, LV dysfunction, young age, and definite disease by Task Force criteria. However, ICD therapy does not reduce the frequency of recurrent arrhythmias and antiarrhythmic pharmacological therapy or catheter ablation of VT is prescribed to diminish the risk of arrhythmic events and death. Frequent shocks are associated with psychological effects and decreased quality of life and every effort needs to be made to reduce their frequency.

## 1.1.2. Antiarrhythmic Pharmacological Treatment in ARVC

Beta-blockers are currently recommended for all patients with ARVC, for both prevention of arrhythmias and reduction of right ventricular wall stress (Corrado et al. 2015). In patients with ventricular arrhythmias, antiarrhythmic drug therapy offers the potential to ameliorate symptoms, although there is no proof that it confers protection against sudden cardiac death (Ermakov and Scheinman 2015, Corrado 2017). Analysis of the effects of antiarrhythmic medications in 95 patients from the North American ARVC Registry (Marcus G et al. 2009) showed that 61% received beta-blockers, and these medications were not associated with an increased or decreased risk of ventricular arrhythmias. Sotalol was associated with a greater risk of any clinically relevant ventricular arrhythmia as defined by sustained ventricular tachycardia or ICD therapy (hazard ratio [HR]: 2.55, p=0.045), but this was not statistically significant after adjusting

for potential confounders. An increased risk of any ICD shock and first clinically relevant ventricular arrhythmia while the patients were taking sotalol remained significant after multivariable adjustment. Amiodarone seemed to be more effective but there were only 10 patients receiving this medication. An independent analysis of a large cohort from Italy (Mazzanti et al. 2016) showed that none of the arrhythmic medications had a beneficial effect on the rate of events when comparing matched periods before and after administered drugs (Table 1). There is no good data indicating that common antiarrhythmic medications reduce VT/VF in ARVC patients. The same is true for catheter ablation in the analysis shown in Table 1; although some data show that catheter ablation might reduce VTs in select patients (Riley et al. 2010, Santangeli et al. 2015). Therefore there is a great need to explore the efficacy of other antiarrhythmic medications. Experimental data on flecainide are promising.

Treatment	Time	n	Person-Yrs	LAE	Rate	95% CI	p Value
Beta-blockerst	Before	67	218	7	0.032	0.015-0.068	0.107
	After	67	218	15	0.069	0.033-0.145	
Sotalol	Before	37	220	3	0.014	0.003-0.060	0.062
	After	37	220	16	0.073	0.030-0.178	
Amiodarone	Before	15	88	1	0.011	0.002-0.083	0.048
	After	15	88	9	0.102	0.047-0.223	
Ablation	Before	27	170	16	0.094	0.035-0.253	0.644
	After	27	170	20	0.117	0.069-0.200	

 Table 1: Matched- Periods Analysis for the Efficacy of Antiarrhythmic Drugs and Transcatheter

 Ablation (Mazzanti, et.al. 2016).

# 1.1.3. Flecainide

Flecainide is a class 1C antiarrhythmic drug that blocks sodium channels. Flecainide is used to suppress cardiac tachyarrhythmias including paroxysmal atrial fibrillation and supraventricular tachycardia. Flecainide is also used to treat LQT3 patients and patients with Ca2+-mediated, catecholaminergic polymorphic ventricular tachycardia (CPVT). Flecainide can have proarrhythmic effects after myocardial infarction (Echt et al. 1991). These divergent actions result from its physiological and pharmacological actions at multiple, levels of cellular organization (Salvage et al. 2017). These properties of flecainide were studied in murine genetic models with modified Nav channel or intracellular ryanodine receptor (RyR2)-Ca2+ channel function (Watanabe et al. 2009). Flecainide accesses its transmembrane Nav1.5 channel binding site during activated, open states, producing a use-dependent antagonism. Closing either activation or inactivation gates traps flecainide within the pore. An early peak INa related to activation of Nav channels followed by rapid de-activation, causes action potential upstrokes and their propagation. This is diminished in pro-arrhythmic conditions reflecting loss of function of Nav1.5 channels, such as in the Brugada syndrome that may be exacerbated by flecainide. In contrast, the pro-arrhythmic effects attributed to prolonged action potential recovery by abnormal late INaL following gain-of-function modifications of Nav1.5 channels in LQT3 are reduced by flecainide. Anti-arrhythmic effects of flecainide that reduce triggering in CPVT mediated by sarcoplasmic reticular Ca2+ release could arise from its primary actions on Nav channels indirectly decreasing [Ca2+]i by a reduced [Na+]i and/or direct open state antagonism of the RyR2-Ca2+ channel. The consequent [Ca2+]i alterations could also modify action potential propagation velocity and therefore arrhythmic substrate through its actions on Nav1.5 channel function. This is consistent with the paradoxical differences between flecainide actions on Na+ currents, AP conduction and arrhythmogenesis under circumstances of normal and increased RyR2 function.

In a small randomized trial flecainide was effective in reducing ventricular arrhythmias in patients with catecholaminergic polymorphic ventricular tachycardia, a condition linked to RyR2 mutations causing increased SR release and triggered arrhythmias (Kannankeril 2017). This study reported a significant reduction of all forms of ventricular arrhythmias recorded during exercise in CPVT patients. ARVC patients show high prevalence of catecholamine-facilitated focal VT that is associated with ventricular premature beats observed at diagnosis and with induced sustained VT (Philips et al. 2013). Ventricular arrhythmogenicity during isoproterenol testing was further proven by [name] group from Bordeaux who demonstrated that induction of sustained and nonsustained VT episodes by isoproterenol was highly sensitive (91.4%) for ARVC diagnosis in 41 patients with the disorder and predictive of follow-up events (Denis et al. 2014).

Experimental data using a novel murine model with cardiac-specific tamoxifen induced PKP2 deficiency indicate that enhanced triggered activity and increased sarcoplasmic reticulum (SR) calcium release via RyR2 channels could contribute to adrenergic-induced arrhythmias in an experimental model of ARVC (Cerrone et al. 2017, Van Opbergen et al. 2017). This study also reported that flecainide effectively prevented the arrhythmias observed in the experimental animals. Separate preclinical and anecdotal clinical reports also suggest that flecainide, probably through a block of the RyR2 receptor is a promising antiarrhythmic approach in ARVC. The arrhythmia burden was tested in 6 animals in the presence of a single dose of 40 mg/kg of flecainide (Cerrone et al, 2012). In contrast with results in untreated animals, flecainide-treated PKP2-cKO mice showed an absence of ISO-induced arrhythmia burden in the total recording period of 20 minutes. These results further support the notion that arrhythmias in PKP2-cKO animals may result from dysregulation of intracellular calcium cycling via increased RyR2-dependent calcium release.

Recent analysis of 8 ARVC patients with recurrent VT/VF events, who were treated with flecainide after several attempts with other antiarrhythmic medications, showed that 6 out of 8 of these patients had arrhythmias eliminated (Ermakov and Scheinman 2017). It is important to stress that patients with variants other than PKP2 and those cases with no known mutation responded to flecainide in this small series.

Clinical data from the Johns Hopkins Registry (Orgeron et al. 2017), in 312 ARVC patients with ICDs showed that patients with ventricular flutter or VF had frequent VPBs  $\geq$ 1000 /24 hours, with hazard ratio of 4.39 (p=0.016). Other predictors included syncope (HR: 1.85; p=0.021), age  $\leq$ 30 years at presentation (HR: 1.76; p=0.036), and male sex (HR: 1.73; p=0.046). Therefore, treatment with flecainide in patients with frequent VPBs will address a high-risk subset of patients.

## **1.1.4. Significance of Pilot Project**

There is no known effective antiarrhythmic treatment in ARVC patients. Flecainide is a promising option, but there are no clinical trials to prove its efficacy and safety in ARVC patients. The pilot study will assess the effect of flecainide on cardiac arrhythmias detected by long-term ECG monitoring and will provide preliminary data that might lead to a larger study with stringent endpoints consisting of ICD-documented VT, VF or death during long-term follow-up. Assessing safety of this therapy is of major importance in view of the results of the CAST trial that showed increased mortality in patients with ischemic heart disease treated with antiarrhythmic drugs including flecainide (Echt et al. 1991). This is the reason we are taking precautions of including only ARVC patients with ICDs and excluding patients with significant left ventricular dysfunction and significant heart failure, who constitute a small minority of ARVC patients. Importantly, as documented in the secondary analyses from the CAST trial, proarrhythmic effects of flecainide in studied patients with depressed or preserved ejection fraction was eliminated by concomitant administration of beta-blockers (Kennedy et al. 1994: Kennedy 1997). If the pilot study documents a significant reduction in ECG-recorded arrhythmias and if a subsequent trial show long-term

effectiveness of this therapy, it would be a major therapy in the treatment of ARVC patients.

# **1.2.** Purpose of the Study

The primary specific aim of this pilot trial is to determine whether flecainide administration is associated with a significant reduction in the number of ventricular premature beats (VPBs) in ARVC patients with ICDs.

The secondary aims are to:

- 1) Assess safety of flecainide administration with particular emphasis on pro-arrhythmic response measured by:
  - a. VPBs on ECG monitoring
  - b. Nonsustained and sustained VT/VF episodes documented on ICD interrogation
  - c. Effects of flecainide on QRS morphology and duration.
- 2) Assess the effects of flecainide on the number of VT runs in 7-day ECG recordings.
- 3) Assess the effects of flecainide on the frequency of atrial premature beats in 7-day ECG recordings.
- 4) To demonstrate feasibility of enrollment of rare arrhythmia ARVC patients in a randomized study in preparation for the planned future large clinical trial with VT/VF as the primary endpoint.

# 2. STUDY DESIGN

## 2.1. Overview

This is a randomized double-blinded placebo-controlled crossover trial on the effect of flecainide on the frequency of ventricular arrhythmias of 38 ARVC patients. The crossover design requires a 10-week treatment with each patient receiving flecainide 100 mg bid and placebo in a blinded randomized order.

## 2.2. Rationale for Study Design

The cross over design of this study is suitable for the ARVC population, as the disease is chronic and the proposed intervention is not curative for the disease. The innovation of this trial is the concept of randomized trial in ARVC patients to test antiarrhythmic therapy. To date there has not been a randomized trial in ARVC patients to evaluate any therapy including ICD therapy, ventricular tachycardia ablation, or pharmacological drugs. As indicated, prior publications regarding pharmacological therapies including antiarrhythmic therapies have shown conflicting results.

## 2.3. Rationale for Dosage

Based on clinical experience and safety profile of flecainide a uniform dose of 100 mg of flecainide bid will be used. This dose is recommended in FDA-approved prescription information. This also was initial dose in the catecholaminergic polymorphic ventricular tachycardia trial although the median dose was 150mg bid (Kannankeril 2017). In the study "Safety and efficacy of flecainide in subjects with Long QT-3 syndrome with delta KPQ mutation" (Moss et al. 2005) an average 100 mg per day dose produced significant effects on late sodium current that caused significant QTc shortening.

# 3. CHARACTERISTICS OF THE RESEARCH POPULATION

## 3.1. Subject Characteristics

- a) **Number of Subjects:** This trial will enroll 38 subjects at 10 enrolling sites who meet study inclusion and exclusion criteria as described in Section 3.2.
- b) Gender and Age of Subjects: Male or female subjects aged 18 years or older.
- c) Racial and Ethnic Origin: There are no restrictions on race or ethnicity in this study.

# 3.2. Inclusion and Exclusion Criteria

Inclusion criteria:

- Age > 18 years.
- Subjects who have been diagnosed with ARVC and meet 2010 Modified Task Force Criteria for ARVC as affected.
- At minimum 500 VPBs on the most recent 24-hour Holter monitor recording prior to consent or after consent if a subsequent recording is required after 5 day washout following discontinuation of anti-arrhythmic medication.
- Functioning implanted cardioverter defibrillator with remote interrogation capability.
- Subjects should be on a beta-blocker including metoprolol, propranolol, atenolol, nadolol, carvedilol or bisoprolol unless contraindication to beta-blockers exists.
- Persons prescribed quinidine, procainamide, propafenone, disopyramide, dronedarone phenytoin, mexilitene, may be included after 5 day washout period with subsequent 24-hour Holter obtained after washout period.
- Persons prescribed sotalol may be included after 5 day washout period during which another beta-blocker may be administered with subsequent 24-hour Holter obtained.
- Subject and personal physician and or cardiologist must agree not to use any antiarrhythmic medications during the 10 weeks of participation, unless needed for management of life-threatening arrhythmias.
- All subjects must agree to use medically acceptable contraceptive measures during participation unless documented as surgically sterile or post-menopausal (no menstrual periods for more than one year).

## Exclusion criteria:

- Prescribed amiodarone or dofetilide at the time of consent.
- Left ventricular ejection fraction ≤40% by any imaging modality: echocardiography, angiography, CMRI, or cardiac nuclear test on the most recent test.
- NYHA heart failure class III or IV at time of consent.
- Prior myocardial infarction at any time in the past.
- Pacemaker dependent rhythm at the time of consent.
- Renal impairment (GFR <30 mL/min/m2).
- Prior diagnosis of severe hepatic impairment.
- Pregnant or plan to become pregnant during the course of the trial (Flecainide has not been adequately studied in pregnant women). Pregnancy test is required for women of child-bearing potential prior to randomization.
- Participating in any other interventional clinical trial.
- Unwilling or unable to cooperate with the protocol.
- Lives at such a distance from the clinic that travel for the consent visit would be unusually difficult.
- Decisionally impaired adults, those of questionable capacity, those who cannot manage taking the study drug per the prescribed regimen, and those who cannot consent for themselves will not be recruited for this study.
- Unwilling to sign the consent for participation.

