#### Table 2. Schedule of Activities.

	Visit	Visit	Visit 2	Visit	Visit	Visit	Visit	Visit	Visit	Visit	Visit
	0 a Screen	1 a Ran- domize	Drug Initia- tion	3	4	5	6 Second Drug Bottle	7	8	9	10 Close- out
Start Medication Weeks	-4-0 weeks	-4-0 weeks	0	1 week + 2 days	3 weeks + 2 days	4 weeks + 2 days	5 weeks + 2 days	6 weeks + 2 days	8 weeks + 2 days	9 weeks + 2 days	10 weeks + 2 days
In person visit	Yes in clinic	No	No By phone	No by phone	In home or in clinic d	No by phone	No by phone	No by phone	In home or in clinic d	No by phone	No by phone
Study Periods			Period	1			Period 2	2			
Informed Consent	√										
Pregnancy Test b	√										
Medical History	√										
Holter Monitor c	✓										
ECG	✓				✓				✓		
Randomization		✓									
Blood Sample					√				✓		
7-day ECG Monitor					√				✓		
Remote ICD interrogation				√				✓			✓
Adverse event				✓	√	✓	√	✓	✓	√	✓
Drug Dispense/Accountability			~				~			~	
Stop and return study drug and ZIO-Patch						~				~	
Study Closeout											✓

a - Visits 0 and 1 could be done on the same day.

b - Pregnancy test must be obtained prior to randomization

c – Holter Monitor for subjects have had a washout of antiarrhythmic therapy

d - Visit at home will be done by specialized services with: ECG recording and blood draw; ZIO-Patch could be self-applied by

subject or by study staff member. These visits could take place in a clinic if this is what subject and investigator are agreeable to.

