# 5.1. Visits

## 5.1.1. Visit 0: Subject Screening and Consent

Each potential subject will have inclusion and exclusion criteria verified by study personnel prior to approaching a potential subject for consent. The consent process begins with the protocol described to them by one of the physicians or research coordinators at the enrolling site. Potential subjects will sit down with the coordinator or physician and have the opportunity to ask questions. Those who meet inclusion/exclusion criteria will then be asked to sign consent for study participation. At this time they will sign an "informed consent" form that is fully approved by the local IRB following local IRB consent administration regulations. It is the responsibility of the investigator to ensure that subjects are eligible to participate in the study prior to enrollment and throughout the study. Once informed consent has been obtained, all screening tests and procedures have been assessed and study eligibility has been confirmed, subjects will be assigned a unique subject identification number. The enrolling site will enter data in the web base system and the system will assign the subject ID after study eligibility criteria are met. The scheme for assigning subject ID is as follow: first 2 numbers are assigned for enrolling site and will not change for duration of the study. Next two numbers are specific to a randomized subject in the enrolling site.

The principal investigator ensures that informed consent from each potential research participant will be obtained by an IRB approved consent designee and documented. The following persons may obtain consent: the principal investigator, sub-investigators, or study team members listed on the IRB application form as a consent designee. Each individual who will interact with potential research participants to obtain consent will submit evidence of human subject compliance training per local IRB regulations.

After written informed consent is obtained, a medical history and an ECG will be obtained from the subject. Any woman of childbearing age must have a negative pregnancy urine or blood test prior randomization, unless the woman is surgically sterile or post-menopausal (no menstrual periods for more than one year). Investigators will verify that subjects must use a medically acceptable method of birth control prior to study entry and while participating in the study.

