# **5.1.3. Visit 2: Phone Visit** (within 7 days from Visit 1)

The following tasks will be performed and documented at the Visit 2:

- Enrolling site staff member will confirm receipt of study shipment and review contents with subject.
- Review study drug prescribing regimen, diary and emphasize importance of compliance with subject. Instruct patient to begin taking study drug and record the date of the subject's first dose of study medication.

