# 5.1.7. Visit 6: Phone visit (Five weeks after initiating study drug)

During this follow-up visit:

- Enrolling site will confirm receipt of study shipment and review contents with the subjects. Shipment will include: second bottle of study drug, diary, Zio-Patch with instructions, blood drawing kit and prepaid return envelope for next day delivery via Federal Express.
- Study drug prescribing regimen, diary and importance of compliance will be reviewed with subject.
- Instruct patient to begin taking study drug and record the date of the subject's first dose of study medication from second bottle. Adverse events will be assessed and reported.

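### The only pregnancy test precedes randomization, so women given placebo first start flecainide about 33 to 44 days later (at most 65) with no repeat test

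*Combined protocol and SAP*

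**What the plan says.** Three places in the protocol agree on one test tied to randomization.

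- The exclusion criteria in Section 3.2 state: "Pregnancy test is required for women of child-bearing potential prior to randomization". The reason given there is that flecainide has not been studied well enough in pregnancy.
- Table 2 (Schedule of Activities) has one tick in the pregnancy-test row, at Visit 0. Footnote b reads "Pregnancy test must be obtained prior to randomization" and footnote a reads "Visits 0 and 1 could be done on the same day".
- Section 5.1.1 asks for a negative urine or blood test before randomization.

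The first dose follows Visit 2, a phone visit "within 7 days from Visit 1" (Section 5.1.3). Section 5.2 then gives 28 days of the first treatment, 7 days of washout and 28 days of the second. The second treatment starts at Visit 6, also by phone (Section 5.1.7). The contents of the parcel are listed: "Shipment will include: second bottle of study drug, diary, Zio-Patch with instructions, blood drawing kit and prepaid return envelope". The task for the site is: "Instruct patient to begin taking study drug and record the date of the" first dose from the second bottle. No task list for Visits 2 to 10 mentions a pregnancy test, and the blood drawn at Visits 4 and 8 is for flecainide levels.

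The protocol has other controls. Women who plan a pregnancy are excluded. Section 3.2 adds "All subjects must agree to use medically acceptable contraceptive measures during participation", with exceptions for surgical sterility and menopause, and Section 5.1.1 has investigators verify contraception. Section 5.1.1 also makes the investigator responsible to "ensure that subjects are eligible to participate in the study prior to enrollment and throughout the study". Section 10.2 requires direct questioning about adverse experiences at each visit.

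**The concern.** A test before randomization works as a test before exposure only for women who get flecainide first. For women who get placebo first, the whole of Period 1 and the washout lie between the test and the first active dose. The safeguard therefore protects the two sequences unequally, although the reason for it applies to both.

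Followed exactly as written, the plan can start flecainide in a woman with an undetected early pregnancy. Section 11.1.5 accepts that the risks to an unborn baby cannot be foreseen, and Section 10.1.1 counts fetal distress, fetal death and birth defects as serious adverse events. The point concerns subject safety. It does not touch the primary estimand, the sample size or the power.

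**Working it through.** **Inputs from the protocol**

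- Visits 0 and 1: weeks -4 to 0 relative to first dose, same day permitted (Table 2, Schedule of Activities).
- Visit 2 (first dose, day 0): within 7 days of Visit 1 (Section 5.1.3).
- Visit 4: week 3 ± 2 days. Visit 6: week 5 ± 2 days (Table 2, Schedule of Activities).
- Period 1 of 28 days and washout of 7 days (Section 5.2).

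**The plan's own figure.** 28 + 7 = 35 days = 5 weeks, which matches Visit 6. With the window, the second bottle starts on day 35 - 2 = 33 to day 35 + 2 = 37.

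**Age of the test at first flecainide dose**

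| Path | Placebo first | Flecainide first |
|---|---|---|
| Visits 0 and 1 on the same day, Visit 2 at 0 to 7 days | 33 + 0 = 33 to 37 + 7 = 44 days | 0 to 7 days |
| Same, allowing one day for delivery of bottle 1 | 33 + 1 = 34 to 44 days | 1 to 7 days |
| Outer limit, Visit 0 at day -28 | 37 + 28 = 65 days | 28 days |

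The protocol permits the same-day path but does not require it. An earlier Visit 0 lengthens the interval in both sequences. The 65 days take week -4 as counted from first dose, as the schedule's time row does.

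**Expected number affected.** The documents give neither the number of women of child-bearing potential nor a contraceptive failure rate. Assume that 19 of the 38 subjects get placebo first, that 2 to 8 of these are women of child-bearing potential, and that contraception fails at 1% to 10% a year. Then

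expected conceptions = women × annual failure rate × days / 365

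- Low end: 2 × 0.01 × 33/365 = 0.0018
- High end, same-day path: 8 × 0.10 × 44/365 = 0.096
- High end, outer limit: 8 × 0.10 × 65/365 = 0.142

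**Effect of a repeat test**

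- On the day of Visit 6, before the start instruction: the interval from test to first flecainide falls to 0 days.
- At in-person Visit 4 (day 19 to 23): 33 - 23 = 10 to 37 - 19 = 18 days remain.

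**Do the existing controls detect a pregnancy?** Excluding planned pregnancy and requiring contraception make conception less likely. Adverse-event questioning can bring out a pregnancy that the woman already knows of or suspects. The duty to ensure continuing eligibility names no procedure before the second bottle. None of these finds an early pregnancy without symptoms. The plan also asks for a test on top of contraception at entry, so it does not itself treat contraception as enough.

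**The case against.** The best case against the point is about weight. The sections on pregnancy testing agree with one another, so no rule in the plan is broken. Contraception is mandatory and verified, and pregnancy is an exclusion criterion under the continuing-eligibility duty. Staff also speak to the subject at Visits 3, 4, 5 and 6 by the time bottle 2 starts. Even the most pessimistic figure, 0.14, is about one conception in seven such trials, and it rests on assumed inputs. The 65 days need the test at exactly week -4 and Visit 6 at the end of its window.

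A second argument is that a Visit 6 test leaves part of the risk alone, because women in either sequence can conceive during 28 days on flecainide. With the same assumptions doubled to both sequences (4 to 16 women), that is 4 × 0.01 × 28/365 = 0.003 to 16 × 0.10 × 28/365 = 0.12. The repeat test would then address 0.0018/(0.0018 + 0.0031) = 37% to 0.096/(0.096 + 0.123) = 44% of the combined figure on the same-day path. A home test is also self-reported and can miss a very recent conception.

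Most of this stands as a limit on size. The expected number is small, 65 days is an extreme, and contraception remains the only control over conception during dosing. None of it shows that an unrecognised pregnancy would be found before a placebo-first woman starts flecainide. The consent form was not available, so pregnancy-reporting or stopping instructions in it cannot be ruled out. The schedule and the visit task lists still contain no second test.

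**Conclusion.** The concern holds. The protocol schedules one pregnancy test, before randomization. Women allocated to placebo first start flecainide 33 to 44 days after it on the same-day path and up to 65 days after it at the schedule's limit, against 0 to 7 and up to 28 days for women allocated to flecainide first. These intervals follow directly from the protocol's visit windows and are certain.

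The consequence is much less certain: about 0.002 to 0.10 expected conceptions over the whole trial, or 0.14 at the outer limit, on assumed numbers of women and failure rates. This is a change that should be made, because the possible harm is serious and prevention costs little. It is not a threat to the trial's conclusions.

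**What to change.** 1. Add a urine pregnancy test kit to the second shipment for every woman of child-bearing potential, in both sequences so that the blind is kept.
2. At Visit 6, record a negative result before giving the instruction to start the second bottle.
3. Tick the test at Visit 6 in Table 2 (Schedule of Activities), and have footnote b require it both before randomization and before the second bottle.
4. Add a rule that a subject with a positive test does not start the second bottle and stays in follow-up through Visit 10. Section 8.5 covers only a subject who herself chooses not to take study drug. Section 7 covers voluntary withdrawal, loss to follow-up and failure of the Holter criterion.

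If the sponsor prefers a result observed by staff, test at in-person Visit 4, where blood is already drawn, and accept the 10 to 18 days that remain before the second bottle.

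The cost is a short amendment, one kit per eligible woman in a parcel that already goes out, and one line on the Visit 6 form. The result is self-reported by phone, and a conception in the days just before the test can be missed. Rarely, one subject's Period 2 data would be lost; her Period 1 data stay in the Section 14.2 mixed model under its missing-at-random assumption.
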